3 STUDY OBJECTIVES

This study will be conducted in two phases, an exploratory phase and a confirmatory phase. This statistical analysis plan is for the exploratory phase of this study. The exploratory phase of this study will be comprised of a cross-sectional component and a longitudinal component.

3.1 Exploratory Phase, Cross-sectional Objectives

The primary objective of the cross-sectional component is:

- To compare Flortaucipir imaging results in subjects with AD to subjects with MCI and cognitively healthy older individuals

The secondary objective of the cross-sectional component is:

- To establish a database of cognitively healthy individuals to show the spectrum of Flortaucipir imaging results in cognitively healthy individuals across a range of age strata

Exploratory objectives of the cross-sectional component are:

- To determine whether greater degrees of cognitive impairment correlate with higher Flortaucipir uptake in subjects with an amyloid positive status
- To explore whether tests of specific cognitive domains correlate with regional Flortaucipir uptake
- To explore the relationships between Flortaucipir uptake and biomarkers of neurodegeneration and neurological disease (cerebrospinal fluid (CSF) markers including tau, phospho-tau and beta-amyloid (AB), genetic markers, PET amyloid imaging, and brain atrophy assessed by volumetric magnetic resonance imaging (MRI))
- To expand the Flortaucipir safety database

3.2 Exploratory Phase, Longitudinal Objectives

The primary objective of the longitudinal component is:

- To assess the rate of change of tau deposition as measured by Flortaucipir uptake over time

The exploratory objectives of the longitudinal component are:

- To explore associations between changes in Flortaucipir uptake in the brain and clinical and functional measures, as well as, biomarkers of neurodegeneration and neurological disease (CSF markers including tau, phospho-tau and beta-amyloid (AB), genetic markers, PET amyloid imaging, and brain atrophy assessed by volumetric MRI)
- To expand the Flortaucipir safety database

4 STUDY DESIGN

4.1 General Design

This study is an open label, multicenter Phase 2 study. This study is conducted in two phases, an exploratory (first) phase and complimentary (second) phase. The study will enroll cognitively healthy volunteers, subjects with mild cognitive impairment (MCI) and subjects with Alzheimer's disease. Approximately 230 subjects will be enrolled in the study: 80 cognitively healthy volunteers (20 subjects who will be ≥ 20 to ≤ 40 years of age, and 60 subjects who will be ≥ 50 years of age), 80 subjects with MCI, 70 subjects with AD (60 subjects with a Mini-Mental State Examination (MMSE) ≥ 20 , and 10 subjects with an MMSE > 10 and < 20). For the 60 cognitively healthy volunteers ≥ 50 years of age, these subjects will be distributed across age deciles (50-59, 60-69, 70-79 and > 80).

All subjects will provide informed consent before starting any study procedures.

Screening assessments may take place over several days and will include demographic information, cognitive testing, safety assessment, and MRI, including both volumetric and standard clinical sequences. Subjects who qualify for the study will undergo both a florbetapir F 18 PET imaging session and a Flortaucipir PET imaging session. The imaging sessions must be performed at least 48 hours apart, but not more than 60 days apart. The order of the scans is interchangeable. Some subjects, who are ≥ 50 years of age, will have the option to also participate in cerebrospinal fluid (CSF) collection by lumbar puncture (LP).

Subjects who are ≥ 50 years of age will return for have a follow-up visits at 9 (+/-2) months 18 (+/-2) following the initial Flortaucipir scan. Cognitive assessments and updates to concomitant medications and medical history will be collected at each follow-up visit. Subjects will also have follow-up Flortaucipir scans and MRI, including both volumetric and

standard clinical sequences. A sub-set of subjects may have the option to have an additional resting state functional (rsf) MRI sequence scan in addition to the volumetric and standard clinical sequences at both the screening MRI and follow-up MRIs. Subjects or their designated decision maker will be contacted by phone at 5 and 14 months following the initial Flortaucipir scan to collect updated concomitant medications and medical history.

Florbetapir F 18 PET Imaging Session:

For the florbetapir F 18 PET imaging session, an intravenous (IV) catheter will be placed for administration of florbetapir F 18 injection. Subjects will receive a single IV bolus injection target dose of 370 MBq (10 mCi) of florbetapir F 18 injection followed by a saline flush. At approximately 50 minutes following injection, a continuous 10-minute brain scan (2 acquisitions of 5 minute duration) will begin.

Adverse events will be continuously monitored during the florbetapir F 18 PET imaging session. A physician or physician designee must evaluate the subject for adverse events prior to injection and prior to discharge from the imaging center. Subjects who experience an adverse event will not be discharged from the imaging center until the event has resolved or stabilized.

A follow-up phone call to the subject, or designated decision maker, will be conducted between 2 or 3 business days of the post-injection of florbetapir F 18, but not before 48 hours post-injection, to confirm subject well-being and to collect information about any new adverse events. If both of these days are not business days, the follow-up phone call can occur the following business day.

Flortaucipir PET Imaging Session(s):

For the Flortaucipir PET imaging session(s), an IV catheter will be placed for administration of Flortaucipir injection. Subjects will receive a single IV bolus injection target dose of 370 MBq (10 mCi) of Flortaucipir injection followed by a saline flush. At approximately 80 minutes post dose, a continuous 20-minute brain scan (4 acquisitions of 5-minute duration) will be obtained. If at any point during the imaging session it is determined that the subject is not able to continue, or that it is not in the best interest of the subject to continue, imaging will be discontinued. The image data that has been collected up to that point will be analyzed. Clinical laboratory tests will be obtained prior to injection and upon completion of each imaging session. Adverse events will be monitored continuously during the imaging session. Subjects who experience any adverse event during an imaging session will not be discharged until the event has resolved or stabilized.

A follow-up phone call to the subject, or designated decision maker, will be conducted between 2 or 3 business days of the imaging day, but not before 48 hours post-injection, to confirm subject well-being and to collect information about any new adverse events. If both of these days are not business days, the follow-up phone call can occur the following business day.

4.2 Discussion of Study Design

This trial is designed to evaluate the brain tau protein imaging properties and safety of Flortaucipir to be used in subjects with cognitive impairment (first and second phases) and healthy volunteers (first phase only). Subjects will be categorized into groups of AD, MCI, and cognitively normal (CN). Comparing the mean standardized uptake value ratios (SUVr) from each category will support the primary objective of detecting a significant difference of Flortaucipir imaging results among diagnostic groups. CN subjects will also be further stratified by age. This stratification will establish a database of imaging results to collect data on the accumulation of brain tau protein across age ranges. Another goal of this protocol is to establish a relationship between Flortaucipir imaging results and cognitive assessments. Allowing all subjects to complete various cognitive assessments will provide evidence whether greater degrees of cognitive impairment will be correlated with higher levels of Flortaucipir uptake. This relationship is important in this protocol in order to determine the utility and predictive power of Flortaucipir on the severity of cognitive impairment.

4.3 Method of Assignment of Subjects to Treatment Groups

Florbetapir F 18:

All subjects will receive a single IV bolus administration target dose of 370 MBq (10 mCi) of florbetapir F 18 injection.

Flortaucipir:

All subjects except for young cognitive normal (YCN) subjects will receive a single IV bolus administration target dose of 370 MBq (10 mCi) of Flortaucipir injection at each of the baseline, 9 months, and 18 months visits. YCN subjects will only receive a single IV bolus administration of Flortaucipir injection with a target dose of 370 MBQ (10 mCi) at baseline visit.

4.4 Blinding

A blinded design was not used for this trial, because all subjects will receive the same medication.

For the exploratory (first) phase, Avid personnel will not be blinded to longitudinal cognitive data nor to the PET scans (both florbetapir and Flortaucipir). The blinding of imaging and/or clinical information at confirmatory phase will be discussed at confirmatory SAP.

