Subjects who are ≥ 50 years of age will return for follow-up visits at 9 (+/-2) months and 18 (+/-2) months following the initial ¹⁸F-AV-1451 scan. Cognitive assessments and updates to concomitant medications and medical history will be collected at each follow-up visit. Subjects in the Exploratory Phase will also have follow up ¹⁸F-AV-1451 scans and MRI, including both volumetric and standard clinical sequences. A sub-set of subjects in the Exploratory Phase may have the option to have an additional resting state functional (rsf)MRI sequence scan in addition to the volumetric and standard clinical sequences at both the screening MRI and follow-up MRIs. All follow-up procedures should be collected within the specified visit window (See Section 7.1.4). Subjects or their designated decision maker will be contacted by phone at 5 and 14 months following the initial ¹⁸F-AV-1451 scan to collect updated concomitant medications and medical history.

Avid personnel will be blinded to the Confirmatory Phase longitudinal cognitive data. Avid personnel will also remain blinded to the PET scans (both florbetapir and ¹⁸F-AV-1451) performed on subjects in the Confirmatory Phase with the exception of periodic quality assurance (QA) assessments of a random subset of image data (not to exceed 20% unless issues identified that warrant additional review). These QA reviews will serve to ensure image quality and data integrity for the scans collected and managed by the imaging core laboratory. Avid staff performing the PET scan QA assessment will not be aware of diagnostic group or cognitive test scores for the subjects/images being reviewed.

Florbetapir F 18 PET Imaging Session:

For the florbetapir F 18 PET imaging session, an intravenous catheter will be placed for IV administration of Florbetapir F 18 Injection. Subjects will receive a single IV bolus injection target dose of 370 MBq (10 mCi) of Florbetapir F 18 Injection followed by a saline flush. At approximately 50 minutes following injection, a continuous 10-minute brain scan (2 acquisitions of 5 minute duration) will begin.

Adverse events will be continuously monitored during the florbetapir F 18 PET imaging session. A physician or physician designee must evaluate the subject for adverse events prior to injection and prior to discharge from the imaging center. Subjects who experience an adverse event will not be discharged from the imaging center until the event has resolved or stabilized.

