8.1.1.2. Confirmatory Phase

The final hypothesis and endpoint measurements for the Confirmatory Phase are yet to be determined and will depend on the discoveries from Exploratory Phase data. However the primary objective of the confirmatory phase is to validate the accuracy of ¹⁸F-AV-1451 scans to predict clinically significant disease progression within 18 months from scan (e.g., cognitive function deterioration as measured by endpoints based on Exploratory Phase results). For the purpose of sample size calculation, we assumed that the target success criteria would be at least 70% sensitivity and at least 70% specificity for ¹⁸F-AV-1451 scans to detect this deterioration, with the lower bound of 95% confidence intervals (CI) above 50% for both sensitivity and specificity. Preliminary analysis of the exploratory phase cohort data showed that clinical assessments may have a relatively large variance. It is important to ensure that enough subjects will be in each group for sensitivity and specificity calculation (i.e., the subjects with or without a significant disease progression). To that end, we assume at least 20% of the subjects will be in each group at the 18 month follow up. With this assumption, a 5% two-sided type I error rate,

and that 95% CI will be calculated using Wilson score method, a sample of 115 subjects will provide an over 90% probability to observe lower bound of 95% CI above 50%, for both sensitivity and specificity. Also assuming an approximate 20% drop out rate over the 18 months follow up, this study will aim to enroll 150 subjects in total.

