8.1.4. Confirmatory Phase

Longitudinal data from the exploratory study phase will be assessed periodically to determine the relationships between various ¹⁸F-AV-1451 imaging parameters (e.g., composite and regional SUV_r, voxel based statistics and visual interpretation) and the change from baseline in the various cognitive and functional assessments. These data will be used to generate hypotheses regarding the relationship between ¹⁸F-AV-1451 PET tau imaging and cognitive/functional change that will be formally incorporated into an analysis plan and tested in the confirmatory stage of the study.

Based on discoveries using data from Exploratory Phase, a disease progression measurement will be chosen as truth standard (TS), and the accuracy of ¹⁸F-AV-1451 PET scans to detect this TS within 18 months of scan will be evaluated. Hypothesis testing and detailed analyses will be described in a statistical analysis plan (SAP), which will be finalized prior to database lock. Possible analyses include calculation of accuracy measures such as sensitivity, specificity, and two sided 95% confidence intervals (CI) around these rates. Other analyses may include Mixed-Effect Model Repeated Measures (MMRM) analysis, risk ratio analysis, and time to event analysis.

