6.4.1.2 Qualitative assessment for Flortaucipir and Diagnostic Performance

At the exploratory phase, the baseline flortaucipir scan images will be visually interpreted by Avid's imaging experts. The scans will be classified as either

- AD pattern (AD+)
- AD pattern and likely to progress (AD++)
- Not consistent with an AD pattern (AD-)

AD++ also is referenced as Tau+ in the SAP, and the rest is referenced as Tau-.

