6.4.2 Secondary Efficacy Variables

6.4.2.1 Amyloid Beta Status Based on Florbetapir

Florbetapir F 18 images will be assessed by expert readers blinded to the diagnostic group for the subjects. The images will then be classified as either AB+ (amyloid positive) or AB- (amyloid negative). For images read by more than one reader, the majority or consensus read will be used for each subject.

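### Baseline flortaucipir scans are graded for likely progression by sponsor staff whom the SAP leaves unblinded to follow-up cognition, with no masking or read-timing rule, so AD++ accuracy figures may be inflated

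*SAP*

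**What the plan says.** **Who can see what.** For the exploratory phase, SAP 4.4 states that "Avid personnel will not be blinded to longitudinal cognitive data nor to the PET scans (both florbetapir and Flortaucipir"). The reason it gives for having no blinding is that every subject receives the same medication.

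**Who reads.** Under SAP 6.4.1.2, "the baseline flortaucipir scan images will be visually interpreted by" the sponsor's imaging experts. There are three grades: not an AD pattern (AD-), AD pattern (AD+), and AD pattern with progression judged likely (AD++). Only AD++ counts as Tau+. The section says nothing about masking, the order of reads, their date or when they are locked.

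**How other reads are handled.** In SAP 6.4.2.1, florbetapir images are "assessed by expert readers blinded to the diagnostic group for the subjects". For confirmatory-phase quality checks, Protocol 5.1 says "Avid staff performing the PET scan QA assessment will not be aware of diagnostic group or cognitive test scores".

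**Where the read is used.** AD++ status is the predictor in these analyses:
- the repeated-measures models and the CDR-SB ANCOVA (SAP 8.6.2.4.1);
- the rate ratios (8.6.2.4.2);
- the CDR trend test (8.6.2.4.3);
- the sensitivity, specificity, predictive-value, likelihood-ratio and relative-risk tables (8.6.2.4.4).

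SAP 8.6.1.1 also tabulates the visual grades against diagnosis and amyloid status.

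**The concern.** AD++ asks the reader to forecast decline. If the reader can know the decline, the diagnosis or the amyloid result, the read no longer predicts independently of what it is tested against. That all subjects receive the same tracer does not address this, because the risk lies with the reader and not with treatment.

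Access to outcomes is a realistic possibility. Protocol 8.1.4 plans that "Longitudinal data from the exploratory study phase will be assessed periodically to determine the relationships between various" imaging parameters, visual interpretation among them, and cognitive change. Protocol 8.1.1.2 reports that "Preliminary analysis of the exploratory phase cohort data showed that clinical assessments may have a relatively large variance", so some exploratory clinical data had been analysed by Amendment 2. SAP 5.2 refers to that amendment, so the SAP came later.

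Two things are at stake. The first is the exploratory AD++ accuracy, rate-ratio and mean-difference figures themselves. The second is two decisions that rest on exploratory results: the confirmatory truth standard (Protocol 8.1.4) and the primary confirmatory image method (Protocol 8.3).

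**Working it through.** **Comparing the passages**

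| Visual assessment | Who | Masking stated |
|---|---|---|
| Florbetapir read (SAP 6.4.2.1) | Expert readers | To diagnostic group |
| Confirmatory PET quality check (Protocol 5.1) | Sponsor staff | To diagnosis and cognitive scores |
| Exploratory baseline flortaucipir read (SAP 6.4.1.2) | Sponsor imaging experts | None; SAP 4.4 leaves sponsor personnel unblinded |

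The read that forecasts outcome is the one with no stated safeguard.

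**Scale**

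The documents give no accuracy figure for exploratory AD++ reads, so there is nothing to reproduce. What follows is illustration only.

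Inputs:
- 80 MCI + 70 AD = 150 subjects (SAP 4.5).
- 20% dropout, borrowed as an assumption from the confirmatory planning in Protocol 8.1.1.2: 150 × 0.8 = 120 evaluable.
- Progression in 20% (the lower limit in the same section), 30% or 50% (further assumptions): 24, 36 or 60 progressors.

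*One changed read in a progressor* moves sensitivity by 100/24 = 4.2, 100/36 = 2.8 or 100/60 = 1.7 percentage points.

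*Image with no information.* Start with half of each outcome group graded AD++, so sensitivity and specificity are 50%, the relative risk is 1.0 and 60 of 120 reads are discordant with outcome. Then correct discordant reads, in proportion to group size. With A, B = AD++ with and without clinically meaningful change, and C, D = the same for non-AD++, RR = [A/(A+B)] / [C/(C+D)] as in SAP 8.6.2.4.4.

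| Progression | Reads changed | A, B, C, D | Sens / spec | RR | p: Pearson / Fisher / continuity-corrected |
|---|---|---|---|---|---|
| 20% | 13 of 60 (22%) | 15, 38, 9, 58 | 62.5% / 60.4% | 2.11 | 0.043 / 0.065 / 0.073 |
| 30% | 12 of 60 (20%) | 22, 34, 14, 50 | 61.1% / 59.5% | 1.80 | 0.038 / 0.047 / 0.061 |
| 50% | 11 of 60 (18%) | 36, 25, 24, 35 | 60.0% / 58.3% | 1.45 | 0.045 / 0.067 / 0.068 |

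The counts were chosen as the point where the unadjusted Pearson test crosses 0.05. The other tests mostly do not cross it, and SAP 8.6.2.4.4 plans no test for this table. The p-values show scale and nothing more.

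*Image with real information.* If a share f of discordant reads is corrected, apparent accuracy = base + (1 − base) × f. With base 0.60, f = 0.3 gives 0.60 + 0.40 × 0.3 = 0.72.

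| f | Apparent sens and spec | RR, 20% progress | RR, 30% progress | RR, 50% progress |
|---|---|---|---|---|
| 0 | 60% | 1.91 | 1.76 | 1.50 |
| 0.1 | 64% | 2.50 | 2.23 | 1.78 |
| 0.2 | 68% | 3.30 | 2.84 | 2.13 |
| 0.3 | 72% | 4.42 | 3.67 | 2.57 |

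From a base of 70%, the confirmatory target in Protocol 8.1.1.2, the same shares give 73%, 76% and 79%. The percentage-point gain is smaller, but at f = 0.3 the relative risk still rises from 2.33–3.81 to 3.76–7.78 (50% and 20% progression).

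**The case against.** The strongest reply is that the phase is declared hypothesis-generating, the lack of blinding is disclosed, and the AD++ prediction analyses are listed as exploratory. The longitudinal primary analysis (SAP 8.6.2.1) and the cross-sectional group comparisons of means use SUVr, which no reader grades. The confirmatory cohort has separate subjects, blinded cognitive raters and a sponsor blinded to cognition and, apart from quality checks, to scans. Its image method is fixed before its images are analysed. An over-optimistic exploratory result would make confirmation harder and would not create a false one. All of this stands, and it limits the severity.

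It is also true that SAP 4.4 speaks of sponsor personnel in general. No passage says that readers were handed scores, and some reads may predate follow-up data. A masking rule may exist in a document not available here, although the imaging manual in Protocol 7.3 is described as covering image collection. These points mean that bias is unproven. They do not supply the missing rule.

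The share of outcome-informed reads is invented, and the p<0.05 result depends on the test chosen. Both criticisms are fair, and the numbers should be read only as a guide to sensitivity. Nor do the documents show that reader bias would favour one truth standard over another. The effect on the two downstream choices is a risk of undue optimism, without a known direction.

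**Conclusion.** The concern holds. The SAP expressly leaves sponsor personnel unblinded, assigns a prognostic read to sponsor staff, and tests that read against the same subjects' outcomes without masking, dating or locking it. Every AD++-based estimate in SAP 8.6.2.4, and the tabulations of visual grades in 8.6.1.1, are exposed.

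The actual inflation cannot be known from the documents and may be zero. Under the stated assumptions (120 evaluable subjects, 20–50% progressing, up to 30% of discordant reads influenced), a true 60% sensitivity and specificity could appear as up to 72%. This should be fixed, because the AD++ figures cannot otherwise be read as predictive accuracy. It does not threaten the confirmatory test.

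**What to change.** Amend SAP 4.4 and 6.4.1.2 so that:
- the existing sponsor readers grade baseline flortaucipir scans de-identified and in random order;
- they are masked to diagnosis, amyloid result, follow-up scans and all cognitive data;
- the read criteria are fixed beforehand;
- reads are dated and locked before linkage to follow-up, and only these reads enter 8.6.1.1 and 8.6.2.4.

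If the reads were already made masked and before follow-up data existed, document that; no re-read is needed. If unmasked reads exist, repeat them masked. If the AD++ criteria were built on this cohort's outcomes, or readers are likely to remember cases, masked re-reading will not remove the optimism. In that case label the AD++ figures as developmental and do not present them as estimates of predictive accuracy.

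The cost is SAP wording alone if the reads were already masked or are labelled developmental, and otherwise one masked read session. No new reader or scan is needed. The downside is reader time and possibly lower reported accuracy.
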